## 8.10 Central Review v. Investigator on Effectiveness Analysis

The effectiveness-based endpoints will be evaluated both by the treating physician (i.e., PI) as well as the independent Central Review Committee. Both sets of results will be summarized in the final report, with the Central Review Committee results being specified as the primary result for Technique Efficacy, Technical Success, Local Tumor Progression, Other Progression (regional and distant), the smallest/largest ablation zone, and the smallest margin.

## 8.11 Safety Analyses

Perioperative AEs are defined as AEs that occur from the time of subject consent through 30-days post any ablation procedure (i.e., the original ablation as well as any re-ablation) regardless of relationship to the study device or procedure.

Device-/procedure- related AEs are defined as AEs that are deemed related to the study device or procedure 30-days post any ablation procedure (i.e., the original ablation as well as any re-ablation) through the end of the study or early discontinuation.

Serious adverse events (SAEs) will be captured from the time of subject consent through the end of the study or early discontinuation regardless of relationship to the study device or procedure.

The number and percentage of subjects experiencing perioperative AEs, device- and procedure-related AEs, and all SAEs will be summarized by MedDRA system organ class and preferred term. A similar summary will also be provided for all SAEs from Visit 3 (the first post-ablation visit) through Visit 6 (end of study) as well as for the entirety of the study (Visit 1 – Visit 6).

Ninety-five percent confidence intervals may be provided for pre-specified adverse events of interest, which are:

1. Pneumothorax (overall and CTCAE grade  $\geq 2$ )
2. Hemorrhage, bleeding requiring medical intervention (CTCAE grade  $\geq 2$ )
3. Chest wall pain
4. Pleural effusion or emphysema (overall and requiring chest tube drainage)
5. Pneumonia
6. Pulmonary abscess
7. Other lower-tract respiratory infection
8. Bronchopleural fistula.

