5.3 Inclusion Criteria

Subjects satisfying the following criteria will be eligible to participate in this study:

1. Signed informed consent.
2. Subjects \geq 22 years old.
3. Performance status 0-2 (Eastern Cooperative Oncology Group classification [ECOG]).
4. Willing to fulfill all follow-up visit requirements.

5. Subjects with no more than five oligometastatic tumors in no more than three organ sites with no more than three tumors in any single organ.
6. Presence of at least one oligometastatic lung tumor with colorectal, renal, or sarcoma histology where the primary tumor is controlled (in the opinion of the investigator or treating oncologist). Histology should be documented by the following criteria: 1) biopsy of target lesion, if feasible, **or** 2) imaging highly suspicious for metastatic lesion in context of a previous biopsy of the primary or other metastases.
7. Oligometastatic lung tumor(s) planned to be ablated should be \leq 2cm (based on the Screening Visit image), in the outer two-thirds of the lung, and not closer than 1cm to the pleura (including fissures) or contiguous with the pleura. The outer two-thirds is defined as beyond the segmental airway, such that proximal endobronchial soft tissue tumors are avoided.

Note 1: A maximum of two ipsilateral oligometastatic tumors may be ablated during a single session as part of this protocol. The tumor size measurement will be based on the Screening Visit image and does not need to be re-confirmed on the Ablation Day.

Note 2: A maximum of three total oligometastatic lung tumors may be ablated as part of the protocol during the entire study follow-up period.

Note 3: A second or third oligometastatic lung tumor may only be ablated if its planned ablation zone does not overlap with the ablation zone of the previously ablated tumor(s).

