19. Subject who received systemic therapy (e.g., chemotherapy, targeted drug therapy, or immunotherapy) within 14 days prior to the planned study ablation procedure or those who plan to receive systemic therapy before completing the primary endpoint assessment (30 days post-ablation).
20. Uncontrolled hypertension pre-procedure (Visit 2). Defined as systolic blood pressure $\geq 160\text{mmHg}$ and/or diastolic blood pressure $\geq 100\text{mmHg}$ despite pharmacotherapy.
21. Subjects who have participated in an investigational drug or device research study within 30 days of enrollment that would interfere with the primary endpoint of this study.
22. Physical or psychological condition that would impair study participation.
23. Severe neuromuscular disease.
24. Subjects judged unsuitable for study participation by the Investigator for any other reason.

Intra-operative exclusion criteria that lead to stopping a procedure:

25. Inability to tolerate anesthesia.
26. Time of navigation to initiation of ablation longer than 60 minutes, per target tumor.
27. Bleeding estimated to exceed 50cc (visualization via the drainage system) or a Nashville grade 2 or higher intervention is required (see Appendix 2).
28. If the CBCT imaging after a bleeding episode obscures the radiographic visibility of the tumor such that the ablation probe/tumor relationship is not discernable, the procedure should be terminated.
29. Any presenting condition discovered intra-procedurally that in the opinion of the Investigator would make participating in this study not in the subject's best interest.

Note 1: For Exclusion Criterium 26, the procedure may be attempted again at a later time providing there were no other complications other than an extended navigation time.

Note 2: For Exclusion Criteria 27 and 28, the procedure may be attempted again at a later time, once, in the opinion of the physician, the area of bleeding is fully resolved.

Note 3: For any rescheduled ablations, the ablation should be rescheduled as soon as feasible

but no longer than four weeks after the originally scheduled ablation. Other than INR, other pre-ablation assessments do not need to be repeated.

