7.1 Visit 1 – Screening

The screening assessments may occur over several dates within 30 days prior to Visit 2 (Ablation Day), but screening assessments should not be conducted on Visit 2 (Ablation Day).

Subjects will be selected for microwave ablation based on the pre-procedure assessments and the Investigator's interpretation of the clinical picture. Eligible subjects will be provided with the study information, including the ICF.

The following screening assessments will occur prior to the study procedure:

- Subjects must be given ample time to review, ask questions, and sign the ICF.
- PI will review inclusion/exclusion criteria and determine if the subject is eligible to participate in the study.
- Collect demographic information (age at time of Visit 1, sex, race, ethnicity).
- Review and collect medical and surgical history, radiation history, and smoking status.
- Record all relevant prior medications (taken within 30 days of Visit 2), including but not limited to blood thinning/anticoagulants, antiplatelets, opioids, systemic chemotherapy, systemic steroids, immunotherapies, anti-inflammatories, NSAIDs, antibiotics, and medications used to treat adverse events
- Record all concomitant procedures.
- Collect height and body weight for BMI.
- Collect key vitals: blood pressure, heart rate, and pulse oximetry.
- Evaluate ECOG performance status.
- Obtain PFTs, which include Spirometry (e.g., FEV1, FVC, FEV1/FVC, FEF25-75, Peak Expiratory Flow, and Maximum Ventilation Volume), Diffusion Capacity (DLCO), Total Lung Capacity (TLC), Functional Residual Capacity (FRC), and Residual Volume (RV).
- Laboratory tests. If these tests (based on SOC) were completed within 30 days of Visit 2, they do not need to be repeated at the Screening visit:
 - CBC with differentials.
 - Coagulation tests, including APTT and PT per site's SOC. INR is required.
 - Only for women of childbearing potential, complete a pregnancy test per site SOC (urine or serum).
 - Data for any serum-based tumor markers (e.g., CEA and LDH) or molecular profiling on the tumor tissue will be collected, if done as part of site SOC.
- Complete the Numeric Pain Rating Scale.
- Complete two validated quality of life questionnaires: EORTC QLQ-C30 and the lung-specific QLQ-LC13. These questionnaires should be administered in person, during the study visit. However, they may be administered over the phone, when needed.

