The number and percentage of subjects experiencing perioperative AEs (time of consent through 30 days of any ablation procedure), device- and procedure-related AEs (30 days post any ablation procedure through the end of the study or early discontinuation) and all SAEs (time of consent through the end of the study or early discontinuation) will be summarized by MedDRA system organ class and preferred term. A similar summary will also be provided for all SAEs from Visit 3 (the first post-ablation visit) through Visit 6 (end of study) as well as for the entirety of the study (Visit 1 – Visit 6). Ninety-five percent confidence intervals may be provided for pre-specified adverse events of interest, which are:

1. Pneumothorax (overall and CTCAE grade ≥ 2)
2. Hemorrhage, bleeding requiring medical intervention (CTCAE grade ≥ 2)
3. Chest wall pain
4. Pleural effusion or empyema (overall and requiring chest tube drainage)
5. Pneumonia
6. Pulmonary abscess
7. Other lower-tract respiratory infection

8. Bronchopleural fistula.

The Numeric Pain Rating Scale scores will be summarized with methodology consistent to the recommendations of the specific survey. Additional endpoints will be summarized with descriptive statistics.

Plans for Interim Analysis

There are no plans for any formal interim analyses with intent to stop the study early or to modify the study design. However, non-formal interim analyses are planned. The first interim analysis will occur after 20 subjects complete Visit 3 (30 days) and will be descriptive in nature only and will not impact the final analysis. The second interim analysis will occur after all subjects complete Visit 3 (30 days) and will include an evaluation of the primary endpoint against the performance goal as well as provide a summary of all baseline and procedural-related data. A complete summary of all safety-related data observed through the duration of follow-up on all subjects will also be provided. The intent of this analysis will be to support regulatory filing activities where appropriate.

An additional interim analysis may be performed after all subjects have completed Visit 5 (6 months). The final analysis will be completed once all subjects have completed Visit 6 (12 months) and will summarize all endpoints collected during the trial.

Complete details for all planned analyses will be included in the study SAP, which will be finalized prior to database lock.

Analysis of Safety

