Local tumor progression				X	X	X
Other tumor progression (regional or distant)				X	X	X

\*Tumor size, as analyzed by the central review committee, will be used for reporting purposes only. The investigator's assessment of tumor size will be used for inclusion/exclusion purposes.

The study will end when all enrolled and treated subjects have completed the 12-month, post-ablation follow-up period or have withdrawn consent prior to completion. The Sponsor may also stop or pause enrolling new subjects prior to reaching 145 subjects based on either safety events, regulatory feedback, or inability to enroll appropriate subjects.

Table 1: Schedule of Assessments

Visit No.	Visit 1	Visit 2			Visit 3	Visit 4	Visit 5	Visit 6	Unsched. Visit 
Visit	Screening	Pre-Procedure	Intra-Procedure	Post-Procedure	Follow-up	Follow-up	Follow-up	Follow-up	
Interval Windows	≤ 30 days pre-ablation	Day 0	Day 0	Day 0 - Discharge	30 days (-7 to +14 days)	3 months (±2 weeks)	6 months (±1 month)	12 months (±1 month)	
Standard Study Assessments									
Informed Consent	X								
Inclusion / Exclusion Criteria	X	X							
Demographics	X								
Medical / Surgical History 	X								
Concomitant medications 	X	X		X	X	X	X	X	X
Concomitant procedures	X	X		X	X	X	X	X	X
BMI	X								
Key Vitals 	X	X		X	X	X	X	X	
ECOG Status	X	X			X	X	X	X	
Pulmonary function tests (PFTs)	X					X	X	X	
Laboratory Assessments									
Pregnancy test 	X	X							
Coagulation tests 	X	X 							
CBC with differential	X								
Tumor markers/molecular profiling 	X								
Subject Report Outcome Assessments									
Numeric Pain Rating Scale	X	X		X					
Quality of Life Questionnaires 	X				X	X	X	X	
Ablation Assessments									
Ablation procedure details 		X							
Imaging Assessments									
Chest CT 	X 				X 	X	X	X	
Abdomen and Pelvis CT 	X 					X	X	X	

Visit No.	Visit 1	Visit 2			Visit 3	Visit 4	Visit 5	Visit 6	Unsched. Visit 
Visit	Screening	Pre-Procedure	Intra-Procedure	Post-Procedure	Follow-up	Follow-up	Follow-up	Follow-up	
Interval Windows	≤ 30 days pre-ablation	Day 0	Day 0	Day 0 - Discharge	30 days (-7 to +14 days)	3 months (±2 weeks)	6 months (±1 month)	12 months (±1 month)	
Imaging Assessments, Cont.									
Brain MRI 	X					X	X	X	

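### Perioperative AEs are analysed from consent, and no planned table separates onset before the procedure from onset after it

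*SAP*

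**What the plan says.** SAP 8.11 sets the window: "Perioperative AEs are defined as AEs that occur from the time of subject consent through 30-days post any ablation procedure". It applies "regardless of relationship to the study device or procedure". Protocol 10.9 uses the same window for its summary: "perioperative AEs (time of consent through 30 days of any ablation procedure". Protocol 4.2 and 12.0 state that window as the period in which AEs are captured; SAP 8.11 makes it the definition of the tabulated category.

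The reporting rule in SAP 8.11 is: "The number and percentage of subjects experiencing perioperative AEs, device- and procedure-related AEs, and all SAEs will be summarized by MedDRA system organ class" (preferred terms are shown too). It specifies no split at the procedure.

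The schedule in SAP 1 places informed consent at Visit 1, with a window of "≤ 30 days pre-ablation". Protocol 7.1 agrees: "The screening assessments may occur over several dates within 30 days prior to Visit 2 (Ablation Day"). It adds that screening should not take place on the ablation day, so some time between consent and procedure is built into the design.

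**The concern.** A collection window and an analysis window serve different purposes. Collecting AEs from consent is sound practice. Using the same window as the definition of a perioperative rate means that an event occurring before any anesthesia or navigation is counted in the same row as one that follows the ablation.

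This is a single-arm study, so no control group absorbs background events, and the stated aim is to judge benefit against risk. The analysis after all subjects complete Visit 3 is meant to support regulatory filing and includes a full safety summary (SAP 8.12). SAP 8.1 presents all results by region to assess similarity. A rate that includes pre-procedure time does not estimate risk after the procedure, and it can vary between regions with the consent-to-procedure interval in addition to any real difference in procedural risk.

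**Working it through.** The plan states neither a pre-procedure AE rate nor the pre-procedure share of the window, so there is no figure of its own to reproduce.

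**Inputs**
- Window: consent to 30 days after ablation, all-cause (SAP 8.11; Protocol 10.9).
- Consent to on-schedule ablation: at most 30 days (SAP 1, Table 1; Protocol 7.1).
- Subjects: 145 (SAP 7). Safety is analysed in subjects whose ablation was initiated (SAP 6).
- Probability of an AE between consent and procedure: not given; assumed 2% to 10%.
- Probability of a post-procedure AE: not given; assumed 40%, with 20% for comparison.

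**Step 1: share of the index window before the procedure.** Share = pre-days / (pre-days + 30).
- 30-day gap: 30/60 = 50% (30/61 = 49% if day 0 is counted as a post-procedure day).
- 14-day gap: 14/44 = 32%.
- 7-day gap: 7/37 = 19%.
- 30-day gap and a later re-ablation with its own 30 days: 30/90 = 33%.

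**Step 2: does another planned table isolate procedure start to day 30?**
- Device- and procedure-related AEs: the SAP 8.11 category begins only 30 days after ablation, so it leaves that period out. The statistical paragraph of the Protocol summary promises related-AE summaries with no time limit, but the SAP definition does not carry this through.
- SAEs: summarized from Visit 3 to Visit 6 and from Visit 1 to Visit 6. Neither isolates the period.
- AEs of interest, including pneumothorax and hemorrhage: no onset window is stated.

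For non-serious events in days 0 to 30, the all-cause table from consent is the only general summary specified.

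**Step 3: subjects with a pre-procedure AE (gross).** 145 × 0.02 = 2.9 and 145 × 0.10 = 14.5, so about 3 to 15 subjects.

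**Step 4: net effect on the overall rate.** A subject who also has a post-procedure AE would be counted anyway. With independence, net = 145 × pre-rate × (1 − post-rate).
- Post-rate 40%: 145 × 0.02 × 0.60 = 1.7 and 145 × 0.10 × 0.60 = 8.7, so about 2 to 9 subjects. A true 40% would be reported as 1 − 0.60 × 0.98 = 41.2% to 1 − 0.60 × 0.90 = 46%.
- Post-rate 20%: 145 × 0.02 × 0.80 = 2.3 and 145 × 0.10 × 0.80 = 11.6, so about 2 to 12 subjects. A true 20% would be reported as 1 − 0.80 × 0.98 = 21.6% to 1 − 0.80 × 0.90 = 28%.

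In a row for a single preferred term, each subject counted only for a pre-procedure event adds 1/145 = 0.7 percentage points.

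**The case against.** The case for leaving the plan alone has real substance.

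- **The category is labelled honestly.** Both documents say that it runs from consent and is all-cause. Relationship to device and to procedure is recorded separately, and subject listings are planned. This stands: nothing is concealed, and a reader who calls the figure the device's rate goes beyond the text. Listings still do not replace a specified summary.
- **Consequences are limited.** No safety hypothesis or performance goal exists, confidence intervals for the AEs of interest are optional, and the enrollment hold and readmission measures are already tied to the procedure. Extra events can only raise the reported rate. This stands and keeps the point modest. Regional comparison could still be affected in either direction.
- **Day share is not event share, and consent need not fall at day −30.** Protocol 2.0 lets standard-of-care screening precede consent. This stands; 50% is a ceiling on time for an on-schedule index ablation.

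Three stronger readings are tempting but not supported:

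- **That two thirds of the window is pre-procedure.** Protocol 5.4 allows rescheduling "but no longer than four weeks after the originally scheduled ablation", and (30 + 28)/(58 + 30) = 66%. But its notes on rescheduling chiefly concern attempts stopped for long navigation or bleeding, where anesthesia and navigation have already taken place. Those days follow exposure to the study procedure. Only a postponement before any navigation, such as for INR, lengthens the true pre-procedure part.
- **That biopsy complications and chemotherapy toxicity will enter the rate.** Eligibility mentions "biopsy of target lesion, if feasible", with an imaging alternative. Biopsy is not in the schedule and may precede consent. Systemic therapy is barred in the 14 days before ablation, so only late toxicity of earlier therapy with onset after consent could count. Both are possible examples, not documented ones.
- **That differences between sites would reflect the consent interval rather than the device.** The documents support only an added source of variation, and by-site summaries are limited to the primary and selected secondary endpoints.

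**Conclusion.** The point holds as a missing onset split. Followed as written, SAP 8.11 and Protocol 10.9 place events that precede any study procedure in the main early safety table, and no other planned table recovers the risk from procedure start to day 30.

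The time share rests on the documents' own windows. The subject counts rest entirely on the assumed pre- and post-procedure rates and on independence; a reader might take the gross 3 to 15 as the rise in the overall rate, but only the net figure has that meaning.

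Collection from consent is not at fault, and no hypothesis test is affected. This is a worthwhile, inexpensive correction to safety reporting rather than a threat to the primary conclusion.

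**What to change.** Keep AE collection from consent. In SAP 8.11 and Protocol 10.9:

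1. Tabulate perioperative AEs and the AEs of interest by onset from the start of the first study procedure attempt (anesthesia or navigation) through 30 days after the index ablation. State that attempts which are stopped and rescheduled count as the first attempt. Otherwise, bleeding from a stopped navigation would be moved into the pre-procedure table, a loss that the present wide window avoids.
2. Put AEs with onset from consent to that first start in a separate pre-procedure table.
3. Optionally, show AEs within 30 days of later ablations as their own block.

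The cost is a change of wording and one more table. Onset date and procedural phase are already recorded for each AE (Protocol 12.2), and procedure date and time are recorded at Visit 2 (Protocol 7.2), so no new data are needed.

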Safety Endpoint	
Adverse events (AEs) will be assessed from the time of subject consent.
 
 • Perioperative AEs will be captured from the time of subject consent through 30-days post any ablation procedure (i.e., the original ablation as well as any re-ablation) regardless of relationship to the study device or procedure. • AEs that are deemed related to the study device or procedure will be captured 30-days post any ablation procedure (i.e., the original ablation as well as any re-ablation) through the end of the study or early discontinuation. • Serious adverse events (SAEs) will be captured from the time of subject consent through the end of the study or early discontinuation regardless of relationship to the study device or procedure.
Secondary Endpoints	
 • Technical Success: All A0 and A1 ablation classification determinations (complete tumor ablation with a surrounding minimal margin) as assessed by cone beam CT imaging, immediately following the ablation procedure. • Navigational Success: Successful navigation to the targeted peripheral lung tumor(s) as confirmed using cone beam CT (CBCT). • Local Tumor Progression (LTP): Recurrence of originally ablated target tumor(s) within or abutting the ablation zone using 30-day post-ablation imaging as the baseline. • Local Tumor Progression Free Survival (LTPFS): Time from the ablation until local tumor(s) progression (LTP) or death, whichever occurs first. • Progression Free Survival: Time from the original ablation until tumor(s) progression or death, whichever occurs first (includes local, regional, or distant progression). • Disease (cancer) Specific Survival: Time from the original ablation until death from the treated primary malignancy. • Overall Survival: Time from the original ablation until subject

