	
Technical Success, Repeat Ablation Efficacy, and Hospital Readmission Rate will be summarized in a similar manner. Local Tumor Progression, Local Tumor Progression Free Survival, Progression Free Survival, and Overall Survival will be estimated using the Kaplan-Meier method and confidence intervals will be provided.
 
The number and percentage of subjects experiencing device-related AEs will be summarized by the MedDRA system organ class and preferred term. A similar summary will also be provided for procedure-related AEs and all SAEs.
 
Summary statistics will be provided for all other endpoints as defined within the protocol.

Interim Analyses	
The first interim analysis will occur after 20 subjects complete Visit 3 (30 days) and will be descriptive in nature only and will not impact the final analysis.
 
The second interim analysis will occur after all subjects complete Visit 3 (30 days) and will include an evaluation of the primary endpoint against the performance goal as well as provide a summary of all baseline and procedural-related data. A complete summary of all safety-related data observed through the duration of follow-up on all subjects will also be provided. The intent of this analysis will be to support regulatory filing activities where appropriate.
 
An additional interim analysis may be performed after all subjects have completed Visit 5 (6 months).
 
The final analysis will be completed once all subjects have completed Visit 6 (12 months) and will summarize all endpoints collected during the trial.

Time and Events Schedule	See Table 1 on the next page.

Table 1: Schedule of Assessments

Visit No.	Visit 1	Visit 2			Visit 3	Visit 4	Visit 5	Visit 6	Unsched. Visit ²¹
Visit	Screening	Pre-Procedure	Intra-Procedure	Post-Procedure	Follow-up	Follow-up	Follow-up	Follow-up	
Interval Windows	≤ 30 days pre-ablation	Day 0	Day 0	Day 0 - Discharge	30 days (-7 to +14 days)	3 months (±2 weeks)	6 months (±1 month)	12 months (±1 month)	
Standard Study Assessments									
Informed Consent	X								
Inclusion / Exclusion Criteria	X	X							
Demographics	X								
Medical / Surgical History ¹	X								
Concomitant medications ²	X	X		X	X	X	X	X	X
Concomitant procedures	X	X		X	X	X	X	X	X
BMI	X								
Key Vitals ³	X	X		X	X	X	X	X	
ECOG Status	X	X			X	X	X	X	
Pulmonary function tests (PFTs)	X					X	X	X	
Laboratory Assessments									
Pregnancy test ⁴	X	X							
Coagulation tests ⁵	X	X ⁶							
CBC with differential	X								

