7.3 Visit 3 – 30-day Follow-up

Visit 3 occurs 30 days (-7 to +14 days) after the ablation procedure. The subject will visit the study site for the following assessments:

- Document any changes or updates to the subject's relevant concomitant medications (blood thinning/anticoagulants, antiplatelets, opioids, systemic chemotherapy, systemic steroids, immunotherapies, anti-inflammatories, NSAIDs, antibiotics, and medications used to treat adverse events)
- Document any changes or updates to the subject's concomitant procedures.
- Complete two validated quality of life questionnaires: EORTC QLQ-C30 and the lung-specific QLQ-LC13. These questionnaires should be administered in person, during the study visit. However, they may be administered over the phone, when needed.
- Collect key vitals: blood pressure, heart rate, and pulse oximetry.
- Evaluate ECOG performance status.
- Evaluate Technique Efficacy, defined as ablation of the target tumor(s) with the ablation zone completely overlapping or encompassing the entire target tumor(s) using **CT imaging** at 30 days (-7 to +14 days) post the original ablation procedure.
- Record readmission to any hospital for any unplanned reason within 30 days of the ablation. The Investigator will assess the reason for the admission and capture the reason in the clinical database.
- Record any applicable AEs or SAEs:
 - If within 30 days of the ablation procedure, record any AEs or SAEs that may have occurred since the last study visit.
 - If after 30 days of the ablation procedure, record only device- or procedure-related AEs or any SAEs that may have occurred since the last study visit.

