Sponsors must immediately conduct an evaluation of a UADE and report the results of the evaluation to FDA, all reviewing IRBs/ECs, and participating investigators within **10 working days** after the Sponsor first receives notice of the event.

SEVERITY OF ADVERSE EVENTS

It is the Investigator's responsibility to assess the severity of an AE. AE severity in this study will be determined using the current version of the Common Terminology Criteria for Adverse Events (CTCAE). The CTCAE uses Grades 1 through 5 with unique clinical descriptions of severity for each AE based on the general guidelines, provided below. Please note that a change in severity, or grade, may constitute a new reportable AE.

- Grade 1: Mild; asymptomatic or mild symptoms; clinical or diagnostic observations only; intervention not indicated;
- Grade 2: Moderate; minimal, local, or noninvasive intervention indicated; limiting age-appropriate instrumental activities of daily living (ADL);
- Grade 3: Severe or medically significant but not immediately life-threatening; hospitalization or prolongation of hospitalization indicated; disabling; limiting self-care ADL (e.g., bathing, dressing, and undressing, feeding self, using the toilet, taking medications, and not bedridden);
- Grade 4: Life-threatening consequences; urgent intervention indicated; and
- Grade 5: Death related to AE.

Note: A semi-colon indicates "or" within the description of the grade.

RELATIONSHIP OF ADVERSE EVENTS

It is the Investigator's responsibility to assess the relationship between all AEs and SAEs and the study procedure and device. The following guidelines should be used in determining the relationship of an AE to a device, study procedure, or other causality:

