- The discontinuation of the device application (or reduction of the level of activation/exposure) and reintroduction of its use (or increase of the level of activation/exposure), impact on the event (when clinically feasible);
- Other possible causes (e.g., an underlying or concurrent illness/clinical condition and/or an effect of another device, drug, or treatment) have been adequately ruled out;
- Harm to the subject is due to error in use; and
- The event depends on a false result given by the device used for diagnosis, when applicable.

To establish the relatedness, not all the criteria listed above might be met at the same time, depending on the type of device/procedure and the event.

*Indicates definitions of relationship that qualify to be recorded as part of the study for AEs only that occur more than 30-days any ablation procedure. All SAEs, regardless of relationship, will be collected.

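### The related-AE table in SAP 8.11 and Protocol 10.9 starts only at day 30 after ablation, so no planned table gives a device- or procedure-related AE rate through day 30 or for the whole study

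*SAP*

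**What the plan says.** **Collection.** The Safety Endpoint row of the Protocol Summary and Protocol 4.2 and 12.0 have sites record all AEs, whatever the cause, from consent to day 30 after any ablation or re-ablation. For the later period they say "AEs that are deemed related to the study device or procedure will be captured 30-days post any ablation procedure", up to study end. SAEs are recorded throughout. Protocol 7.3 gives sites the matching instruction: "If after 30 days of the ablation procedure, record only device- or procedure-related AEs or any SAEs". The footnote to the relationship table in Protocol 12.1 marks Possible, Probable and Causal as "definitions of relationship that qualify to be recorded as part of the study for AEs only that occur more than 30-days any ablation procedure".

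**Analysis.** SAP 8.11 defines the category as follows: "Device-/procedure- related AEs are defined as AEs that are deemed related to the study device or procedure 30-days post any ablation procedure", continuing to the end of study or early discontinuation. It then plans summaries of three groups: perioperative AEs, related AEs as just defined, and all SAEs. Protocol 10.9 lists the same three groups and describes the second as "device- and procedure-related AEs (30 days post any ablation procedure through the end of the study or early discontinuation".

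**Protocol Summary, Statistical Analyses row.** "The number and percentage of subjects experiencing device-related AEs will be summarized by the MedDRA system organ class and preferred term", followed by "A similar summary will also be provided for procedure-related AEs and all SAEs". No time window is given.

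**Available data.** Protocol 12.1 makes the investigator responsible to "assess the relationship between all AEs and SAEs and the study procedure and device", with no time limit. Protocol 12.2 lists onset date, relationship to the devices and relationship to the procedures among the items to record.

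**The concern.** A rule about which events to collect late in follow-up has become the definition of what counts as related. A programmer working from SAP 8.11 would leave out every related event with onset by day 30. Because the window is tied to any ablation, the same exclusion applies to the 30 days after a re-ablation.

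Safety is part of the primary objective (Protocol 4.0), and the study has one arm. All-cause AEs from consent onward mix background illness with effects of the device and procedure. Without a comparator, the investigator's relationship assessment is the plan's main means of separating the two, and for the period around the ablation it is not tabulated.

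The protocol supplies its own example. In the sponsor's pilot (Protocol 3.0), one subject died two weeks after the procedure, and the death was judged probably related to it. Under SAP 8.11 the corresponding fatal event would fall outside the related-AE table, although the all-SAE table would contain it.

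**Working it through.** The main check is to list every planned output that might supply an early or whole-study related-AE rate.

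| Output | Source | Window | Gives a related-AE rate? |
|---|---|---|---|
| Perioperative AEs | SAP 8.11; Protocol 10.9 | Consent to day 30 after any ablation | No, all causes pooled |
| Device-/procedure-related AEs | SAP 8.11; Protocol 10.9 | Day 30 after any ablation to study end | Yes, late events only |
| All SAEs | SAP 8.11; Protocol 10.9 | Whole study, and Visit 3 to Visit 6 | No, all causes pooled |
| AEs of interest | SAP 8.11; Protocol 10.9 | None stated | No; listed by type of event, intervals optional |
| Pain score, 30-day readmission | SAP 8.9 | Around the procedure | No; different endpoints |
| DSMB review of deaths and severe hemorrhage | Protocol 12.3; SAP 9 | 30 days | No; relatedness judged case by case |
| Safety summary at second interim analysis | SAP 8.12 | Follow-up to date | None named |
| Device-related AEs; procedure-related AEs | Protocol Summary, Statistical Analyses row | None stated | Yes, but period unspecified |

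Only two rows are restricted to related events. One starts at day 30 and the other gives no period. If the definition in SAP 8.11 is applied to the second, it too starts at day 30.

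**Could SAP 8.11 be read more loosely?** Its syntax alone might allow it. Protocol 10.9 does not: it gives the perioperative and related groups consecutive windows that meet at day 30.

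**Denominator.** SAP 7 gives 137 evaluable subjects and 5% dropout: 137/(1 − 0.05) = 144.2, rounded up to 145. This reproduces the planned number, which is used below.

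**Range of the effect (assumed inputs).** Let a be the number of subjects with any related AE, and f the share of them whose related AEs all occur by day 30 after an ablation. A subject with both early and late related AEs still counts in the late table.

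- Whole-study rate = a/145.
- Rate in the table as written = a(1 − f)/145.

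| Assumed a | Whole study | f = 0 | f = 0.5 | f = 1 |
|---|---|---|---|---|
| 14 | 14/145 = 9.7% | 9.7% | 7/145 = 4.8% | 0/145 = 0% |
| 44 | 44/145 = 30.3% | 30.3% | 22/145 = 15.2% | 0/145 = 0% |

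The documents give neither a nor f, so these rows show what the definition can do, not what will happen.

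**Second interim analysis.** It follows Visit 3 of all subjects. The Visit 3 window runs from day 30 − 7 = 23 to day 30 + 14 = 44. A subject whose data end at Visit 3 therefore contributes between 0 and 44 − 30 = 14 days to the related-AE table as written. Subjects treated earlier contribute more.

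**The case against.** The strongest reply is that the plan is a deliberate partition that loses no event: all causes through day 30, related AEs afterwards, and SAEs throughout. The perioperative table contains every early related event, so it bounds the early related rate from above. In an open-label study where the investigator assigns relationship, leading with all-cause early events is defensible. For the gravest early harms relatedness is examined anyway, since a death or severe hemorrhage within 30 days halts enrollment until the DSMB decides whether the ablation caused it. SAP 8.12 also promises a full safety summary at the second interim analysis, which leaves room for a related-AE table.

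Much of this stands. A reader might infer that early harms are hidden, and the documents do not support that. What remains is that an upper bound is not a rate, the DSMB review covers two kinds of event and plans no tabulation, and the interim wording names no related-AE summary.

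A reader might also infer that the Protocol Summary promises a whole-study related-AE table which the SAP contradicts. It does not say so. Its Statistical Analyses row is silent on timing, and the Safety Endpoint row of the same Summary carries the day-30 split, so the row may simply be shorthand. It needs reconciling, but it is not proof of a conflict.

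**Conclusion.** The point holds as a fault in the definition of a safety table. SAP 8.11 and Protocol 10.9, followed as written, exclude related AEs with onset by day 30 of any ablation from the table named for related AEs, and nothing else planned gives a related-AE rate for that period or for the whole study. This rests on the wording and the list of planned outputs, not on any assumed event rate.

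The numerical effect is unknown. A reader might infer a large understatement on the view that procedural harms come early, but the documents give no onset distribution, and the share of affected subjects with early events only could lie anywhere from 0 to 1. No hypothesis test, data collection or event capture is affected. The plan should be corrected because the table's name invites misreading on a primary safety objective and the data for the right table will already exist.

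**What to change.** In SAP 8.11, define device-related and procedure-related AEs by the recorded relationship (Possible, Probable or Causal), regardless of onset. Tabulate each by system organ class and preferred term through day 30 of any ablation and for the whole study, and keep the after-day-30 table with its window in the title. Add a note that non-serious unrelated AEs are not collected after day 30, so that readers do not compare all-cause rates across the two periods.

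At the next protocol amendment, align Protocol 10.9 and the Statistical Analyses row of the Summary. The collection wording in the Safety Endpoint row and in Protocol 4.2 and 12.0 is sound and should stay.

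The cost is one SAP wording change and up to four extra summaries (2 relationships × 2 periods = 4). No new data are needed, since relationship and onset date are already recorded. The SAP change alone delivers the tables and is best made before the second interim analysis, which is meant to support regulatory filing. The protocol wording can wait; an amendment needs IRB/EC approval unless it is purely administrative.

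A separate editorial point in the same list: the fourth AE of interest reads emphysema in SAP 8.11 and empyema in Protocol 10.9, and the two should be reconciled.
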